## **7. STUDY POPULATION AND RECRUITMENT**

Describe who and how many subjects will be invited to participate. Include age, gender and other pertinent information.

Study recruitment will be conducted at Westside Family Health Center sites in New Castle County, using Google ads and Research Match. Westside serves a racially, ethnically, and socioeconomically disadvantaged population of over 27,000 patients. Flyers and handouts will be provided to community organizations, social organizations, and shared at community events. In Phase 1 we will enroll 30 study participants, we anticipate 30-40 people will be screened to identify 30 that meet the inclusion and exclusion criteria. For Phase II we will recruit 30 participants, we anticipate screening 30-40 participants to identify participants that meet the inclusion and exclusion criteria. Westside Family Healthcare will be the primary recruiting site.

Attach all recruitment fliers, letters, or other recruitment materials to be used. If verbal recruitment will be used, please attach a script.

Not Applicable

Describe what exclusionary criteria, if any will be applied.

The study inclusion criteria are as follows: 1) self-reported hypertension; 2) prescribed antihypertensive medication; and 3) age  $\geq$  18 years. The exclusion criteria are: 1) cognitive limitations that limit the ability to provide informed consent; 2) unable to speak or read English and 3) are planning to move during the study period .

Describe what (if any) conditions will result in PI termination of subject participation.

Study subjects will participate in one study visit and will be asked to commit to spending 1-hour viewing the stories and providing feedback. If the participant is unable to spend an hour viewing the stories and providing feedback they will be withdrawn from the study. Participants that are withdrawn from the study will be replaced with new study participants.

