### 5. RESEARCH ABSTRACT

Please provide a brief description in LAY language (understandable to an 8th grade student) of the aims of this project.

The objective of this study is to conduct a pilot study of a storytelling intervention for African Americans with hypertension. We will recruit 30 African Americans with hypertension to view six-eight patient stories and provide feedback on their effectiveness, usefulness, and satisfaction with the stories. [name] was awarded a Penn State Clinical and Translational Science Institute KL2 to develop a hypertension storytelling intervention, HBPStories. For the HBPStories project nine African Americans were filmed sharing their experiences living with and managing hypertension; including, diet and exercise tips, suggestions for locating healthy foods, and motivational stories about successfully controlling hypertension.

We will also elicit feedback from the participants about the best approaches for

delivering a storytelling intervention, and to obtain feedback on the resources and health information that would be helpful to an individual participating in a storytelling intervention.

**6. PROCEDURES** Describe all procedures involving human subjects for this protocol. Include copies of all surveys and research measures.

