**Phase I:** We will recruit 30 African Americans with hypertension from Westside Family Health Center, which has multiple sites in New Castle County, using Google ads and Research Match. The participants will watch the stories and provide feedback on their engagement and satisfaction with the stories, the website, and recommendations for incorporating the stories into a future intervention. We will collect self-reported demographic data including age, gender/gender-identity, income, education, years since hypertension diagnosis, and participants will complete a health literacy screening using the Short-form Health Literacy Survey. The participants will watch the stories on the study website and complete a survey in REDCap. Participants will be asked to watch the eight patient videos (each 2-3 minutes in length) and complete a short 3-5-minute survey after each video. The same survey will be administered after each story (Table 1). We will use a Williams Latin Square to determine the order in which participants will watch the videos. This approach will be used to ensure that videos are not watched in the exact same order by the participants. After providing feedback on the individual stories, the participants will complete a 10-minute survey to gauge overall satisfaction with the stories, engagement, usefulness of the website, and potential uses for future studies. We will use the feedback from the survey to rank which stories were most informative and engaging and select the top six for phase II of the study. Participants will be invited to participate in a 30-minute exit interview to discuss their opinions on the stories, to discuss preferences for a hypertension study, how the stories could be used most effectively, and what type of study would be helpful for them and others managing hypertension. If participants report lack of engagement or satisfaction with the stories, we will ask for their feedback on how we might use the stories to be more helpful and what type of study design would be of interest to them. The study visit will take 1-1.5 hours to complete, and participants will receive a \$20 gift card upon completion of the surveys and an additional \$10 gift card for participating in the exit interview. The study visit will take place in person or via Zoom depending on the preference of the study participants. **Community Advisory Board:** We will invite Phase I participants to volunteer to participate in a community advisory board, we will meet with the community advisory board 2-3 times to request feedback on the findings of the first phase of the study, advice on how to incorporate the feedback from participants into the design of phase 2, and to provide suggestions for the design of Phase II of the study. We will meet with the community-advisory board at the close of the study and develop presentations to summarize the preliminary findings of the study and determine an approach for disseminating the findings of both phases of the study throughout the community. Community Advisory Board Meetings will be held in person and via Zoom. **Phase II:** Twenty participants will engage in a 6-week online storytelling intervention and provide feedback on the effectiveness, engagement, and recommendations for improving the intervention. Participants will complete a 10-item survey in REDCap after viewing the weekly story. The participants will also review the study website and access health materials from the American Heart Association covering topics such as using an electronic pill bottle to manage medication, working out at home, and cooking healthy meals. A list of the survey topics are listed in Table 1. Participants will be expected to spend 30-minutes to an hour each week viewing the stories and study material. Participants will complete a pre- and post-study survey to assess changes in diet, physical activity, and medication adherence during the study.

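### Does Phase II need an explicit exclusion of people who took part in Phase I?

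*Protocol*

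**What the plan says.** Section 7 (Study Population and Recruitment) gives one set of criteria. Inclusion requires self-reported hypertension, a prescribed antihypertensive and adult age. Exclusion reads "The exclusion criteria are: 1) cognitive limitations that limit the ability to provide informed consent; 2) unable to speak or read English and 3"; the third item, where the quote breaks off, is a planned move during the study. Phase II is screened against the same list: "For Phase II we will recruit 30 participants, we anticipate screening 30-40 participants to identify participants that meet the inclusion and exclusion criteria". The recruitment sources are given once, without a split by phase: "Study recruitment will be conducted at Westside Family Health Center sites in New Castle County, using Google ads and Research Match".

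Section 6 (Procedures) links the phases. Phase I participants watch eight stories (section 5 says six to eight), complete a survey after each, and also assess the website. The team will use the results to "rank which stories were most informative and engaging and select the top six for phase II of the study". Phase II participants view the weekly story, complete a 10-item survey after it, and "provide feedback on the effectiveness, engagement, and recommendations for improving the intervention". An exit survey asks about engagement and satisfaction, and a pre/post survey covers diet, activity and medication adherence.

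One continuing role is stated for Phase I participants: "We will invite Phase I participants to volunteer to participate in a community advisory board". The board's tasks include giving suggestions for the Phase II design.

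**The concern.** Read literally, the criteria admit to Phase II someone whose ratings chose the Phase II stories and who may have advised on its design. Such people are eligible, can be reached through the same channels, and are already known to the team. Engagement is one of the qualities on which the stories are ranked, and it is asked about again in Phase II. A crossover participant's engagement and satisfaction feedback would therefore not be independent of the selection step, and their baseline survey would not come from someone new to the stories. If this went unrecorded, favourable Phase II feedback could partly repeat what Phase I had already said. Eligibility is protocol content, so the absence of an SAP does not explain the silence.

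**Working it through.** **No stated figure to reproduce.** The protocol gives no alpha, power, effect size or SD for either phase. The check is a reading of the text plus a sizing exercise.

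**1. Which way the text points**

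| Place | Content | Bearing |
|---|---|---|
| Section 7, criteria | No item on earlier participation | Permits overlap |
| Section 7, recruitment | Phase II has its own recruitment target and its own 30-40 to be screened | Suggests new people; those already screened on the same list would hardly need it |
| Sections 6 and 9 | Separate payment for each phase | Suggests new people |
| Section 15 | Separate consent form and survey for each phase (not shown) | Suggests new people |
| Section 6, advisory board | Only stated continuing role for Phase I participants | Suggests no planned crossover |

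The list is also not a complete statement of who is enrolled. It omits being African American, although sections 5 and 6 define the Phase I population that way. Silence in this list is weak evidence of an intention to admit anyone.

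**2. Share of data per crossover participant**

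Section 6 gives 20 Phase II participants and section 7 gives 30, so both are used.
- n = 20: 20 × 6 = 120 weekly surveys; 6/120 = 5.0%
- n = 30: 30 × 6 = 180 weekly surveys; 6/180 = 3.3%

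These are shares of data, not sizes of bias.

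**3. Prior exposure**

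Overlap between the stories seen and the six selected from eight is at least (seen + 6 − 8): 6 if eight were seen, 4 if six were seen. At 2-3 minutes each, that is 4 × 2 = 8 to 6 × 3 = 18 minutes of earlier viewing. Phase II asks for 6 × 30 = 180 to 6 × 60 = 360 minutes. Dilution of the pre/post change is probably small, but the documents do not allow it to be computed.

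**4. Selection carry-over into Phase II ratings**

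Assumptions not in the documents: person-by-story rating noise with SD 1; 30 Phase I raters; the top six of eight stories kept by mean rating; correlation ρ of 0.3 to 0.9 between a person's Phase I and Phase II noise for the same story; a fraction f of Phase II participants drawn from Phase I.

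If all eight stories are truly equal, the two lowest of eight standard normal values have expectations −1.4236 and −0.8522. The top six then exceed the true mean in Phase I by

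(1.4236 + 0.8522) / 6 / √30 = 0.3793 / 5.477 = 0.069 SD.

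The expected carry-over into Phase II is about f × ρ × 0.069. A simulation with 4,000 runs per setting agrees:

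| Overlap f | Formula, ρ = 0.3 to 0.9 | Simulated, n = 20 and 30 |
|---|---|---|
| 0 | 0 | 0.000 |
| 25% | 0.005 to 0.016 | 0.005 to 0.017 |
| 50% | 0.010 to 0.031 | 0.009 to 0.032 |
| 100% | 0.021 to 0.062 | 0.020 to 0.063 |

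If the stories truly differ, with a between-story SD of 0.2, the largest simulated value falls to 0.042.

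**5. Can crossovers be identified?**

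Section 10 says that participants are not anonymous to the researchers, that data are entered under ID numbers, and that identifiers are kept until three years after completion. Matching 30 Phase I enrollees against 20 or 30 Phase II enrollees within one team is feasible without a new screening item. That the team would keep the link across phases is an inference; the protocol does not say so.

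**The case for a change.** The strongest case for a change is that it is nearly free. One exclusion and one screening question would settle the matter, and losing about 30 people from a clinic base of over 27,000, plus ads and a registry, costs nothing that matters. Separate screening counts and consent forms suggest new recruits but do not require them. The calculation above covers only selection; it leaves out familiarity with the stories and the chance that the keenest Phase I participants volunteer again.

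Much of this stands. The criteria are silent, the sentence would be harmless, and the documents give nothing from which to size familiarity or self-selection. It does not show that the plan is wrong, though. No claim in this formative pilot uses Phase II to confirm the Phase I ranking. It is also uncertain how far Phase II re-rates individual stories: section 6 describes its feedback as about the intervention, and the items of the weekly survey are not shown. The proposed remedy would accept either excluding such people or admitting and flagging them, and if both are acceptable the present design is unspecific rather than mistaken. Finally, it is not so that crossover responses could never be separated, since participants are identifiable to the team.

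**Conclusion.** The concern does not call for a change. The criteria leave unsaid whether Phase I participants may enter Phase II, but the surrounding text points to new recruits, and no stated test, comparison or conclusion depends on independence between the phases. Under the assumptions above, selection carry-over is at most about 0.06 rating SD with complete overlap and at most 0.017 at one quarter overlap. Overlap itself is unknown and may be zero. Familiarity and self-selection remain unsized. If crossover did occur, the team could identify it from its own records and report Phase II feedback with and without those people, an analysis detail that a protocol commonly leaves to the SAP. The conclusion rests on Phase II being read as the protocol presents it, as formative feedback; it would need another look if Phase II were later offered as independent confirmation of the story ranking.

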
Participants will receive \$5 dollars for each week for a total of \$30 dollars and will receive a free blood pressure monitor. We will complete exit surveys with Phase 2 Study participants to ask about engagement, reasons for not participating/dropping out, satisfaction with the intervention, and approaches for improving the intervention.

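### Phase I withdraws and replaces participants who cannot give an hour, with no provision to count them or ask why, so engagement and satisfaction may describe completers only

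*Protocol*

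**What the plan says.** The rule is in section 7 of the protocol, under the conditions for ending a subject's participation. That paragraph describes one study visit, so it concerns Phase I. It reads "If the participant is unable to spend an hour viewing the stories and providing feedback they will be withdrawn from the study", followed directly by "Participants that are withdrawn from the study will be replaced with new study participants". The enrolment target for Phase I is 30.

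The Phase I procedures in section 6 set out the visit: "Participants will be asked to watch the eight patient videos (each 2-3 minutes in length) and complete a short 3-5-minute survey after each video". A 10-minute survey on overall satisfaction, engagement and the website follows, and then an invitation to a 30-minute exit interview. The stated duration is "The study visit will take 1-1.5 hours to complete". People who are not engaged are to be heard: "If participants report lack of engagement or satisfaction with the stories, we will ask for their feedback". Payment depends on finishing, as a "gift card upon completion of the surveys".

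For Phase II, the exit survey covers "reasons for not participating/dropping out, satisfaction with the intervention". Phase I has no counterpart.

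**The concern.** Engagement and satisfaction are what Phase I sets out to measure. One reason a person may not give the hour is that the stories do not hold their attention. The rule treats that person exactly like someone with a clash of appointments: both leave the study and both are replaced. Where the first kind occurs, the sample is selected partly on the quantity it is meant to estimate.

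The provision for hearing from disengaged people may not reach them. The overall survey comes after the eight story surveys, and the exit interview comes last, so someone withdrawn partway through may reach neither.

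Two things are at stake. Engagement and satisfaction may be reported for completers as if they described everyone who began. The team may also lose an inexpensive record of how many people did not finish and why, in a study that calls itself a pilot (section 5) and whose protocol file is titled a feasibility study (section 15).

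**Working it through.** The protocol states no completion rate, withdrawal rate, rating scale or SD, so there is no figure of its own to reproduce. Three checks apply.

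**1. Can the hour bind?** Inputs from section 6: eight videos of 2 to 3 minutes, eight surveys of 3 to 5 minutes, one overall survey of 10 minutes. The exit interview is left out because it is by invitation. The demographic questions and the literacy screen are left out because no duration is given.

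- Shortest: 8 × (2 + 3) + 10 = 50 minutes.
- Longest: 8 × (3 + 5) + 10 = 74 minutes.

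Sixty minutes lies inside this range. It does not contradict the stated visit length, but it is not the same as finishing. A quick participant could complete everything in 50 minutes, and a slow one could give the full hour and still have surveys left. Payment is tied to completing the surveys; continued participation is tied to the hour.

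**2. What is provided for those who stop?**

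| | Phase I | Phase II |
|---|---|---|
| Withdrawn if the time cannot be given | Yes (section 7) | Not stated |
| Replaced | Yes (section 7) | Not stated |
| Reasons for dropping out asked | No provision | Yes (section 6) |
| Count of those who stop | No provision | Not stated |
| Ratings given before stopping | No provision | Not stated |

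**3. How large could the effect be?** Let *w* be the number who start and are replaced, and *D* the difference in mean rating between completers and those who stop.

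- Completion among starters = 30 / (30 + *w*). Among the retained records it is 30/30, whatever *w* is.
- Upward bias in a mean rating = *w* / (30 + *w*) × *D*.

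Neither *w* nor *D* can be taken from the protocol. The values below are assumptions that show only how the formula behaves.

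| *w* (assumed) | Share stopping | Bias, *D* = 0 | Bias, *D* = 0.5 SD | Bias, *D* = 1 SD |
|---|---|---|---|---|
| 3 | 3/33 = 9% | 0 | 0.05 SD | 0.09 SD |
| 6 | 6/36 = 17% | 0 | 0.08 SD | 0.17 SD |
| 10 | 10/40 = 25% | 0 | 0.13 SD | 0.25 SD |

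For comparison, the standard error of a mean of 30 is 1/√30 = 0.18 SD. Only the last cell exceeds it.

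The story ranking compares eight ratings given by the same person. A participant who is generally more favourable tends to raise all eight, so the order should change little.

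**The case against.** The strongest reply is that the text says less than a suspicious reader hears. Several stronger readings are tempting, and the protocol does not support them.

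- **That non-completion is concealed.** Section 7 says withdrawn people are replaced. It does not say that they go uncounted, that their ratings are deleted, or that completion will be reported as 30 out of 30. A log may exist, and denominators are often left to an analysis plan. This stands against any claim of concealment. It does not remove the point: an analysis plan cannot recover reasons or overall-survey answers that were never collected.
- **That those removed are bored early leavers.** Section 7 first asks for a commitment of an hour, so being unable to give it may be simply a matter of availability, perhaps settled before the session begins. On that reading the bias is about zero. The text does not say which reading applies.
- **That up to 10 withdrawals are expected.** The protocol says "we anticipate 30-40 people will be screened to identify 30 that meet the inclusion and exclusion criteria". That forecasts how many people must be checked for eligibility and says nothing about stopping after enrolment.
- **That Phase II feasibility is misjudged.** Phase II has no eight-story sitting. It uses six stories, one a week, so completion of the Phase I visit says little directly about it.
- **That the wrong stories will be chosen.** Choosing six of the eight is a within-person comparison and is probably little affected.

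It is also fair to say that asking about dropout suits a six-week programme better than a single visit. The contrast between the phases is therefore not an inconsistency. It shows only that the team already treats such reasons as useful.

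**Conclusion.** The point holds in a limited form. The protocol fixes a rule that can restrict the Phase I engagement and satisfaction results to people who could give the hour, and it provides no means of telling whether that matters. The rule can bind, because the required tasks take 50 to 74 minutes.

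The direction of any bias is upward only if some participants stop because they are less interested or less satisfied. This is plausible but not shown. The size is unknown; the assumed values above suggest it would usually be modest beside the sampling error of 30 people. The conclusion concerns the absolute levels of engagement and satisfaction and the record of who stopped. It does not extend to the story ranking or to Phase II.

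**What to change.** Keep the target of 30 full records and amend the withdrawal paragraph in section 7, for the Phase I visit, so that:

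- everyone who starts the visit is counted in the completion denominator;
- the reason for stopping is recorded, for example time, access, content or loss of interest;
- story ratings already given are kept, unless the participant asks for their removal;
- replacements may still be enrolled and are reported as additional enrolees.

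Present the engagement and satisfaction results alongside the numbers who started, stopped and were replaced. The Phase I consent wording should match.

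The cost is slight extra record-keeping, a few partial records to handle, and a completion figure that may look less favourable. The change is best made before Phase I enrolment. If enrolment has begun, recording can start at once.

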## **8. RISKS AND BENEFITS**

List all potential physical, psychological, social, financial or legal risks to subjects (risks listed here should be included on the consent form).

Potential risk to the subject includes psychological discomfort while watching the videos and self-reflection. Loss of confidentiality is also a risk.

In your opinion, are risks listed above minimal\* or more than minimal? If more than minimal, please justify why risks are reasonable in relation to anticipated direct or future benefits.

This is a minimal risk study.

What steps will be taken to minimize risks?

Provide participants with an overview of what topics will be covered and the study process during the consenting process. Participants will be invited to withdraw if the topics discussed in the videos are upsetting to them.

Describe any potential direct benefits to participants.

There are no direct benefits to the participants.

Describe any potential future benefits to this class of participants, others, or society.

The information obtained from the study participants will be useful in developing other programs and projects for African Americans living with hypertension. We anticipate the participants recruited from this arm of the study will be representative of the Harrisburg community and their experiences may be similar to other patients living with hypertension in other areas in the United States.

If there is a Data Monitoring Committee (DMC) in place for this project, please describe when and how often it meets.

No

